9.5.3 Appropriateness of Measurements

All clinical assessments are standard measurements commonly used in studies of AD.

Standard safety assessments incorporated into this protocol include assessment of AEs and SAEs, measurement of vital signs, clinical laboratory assessments, physical examinations (including dermatologic review), neurologic examinations, ECG measurements, assessments of suicidal thinking and behavior, and MRI.

9.5.4 Reporting of Serious Adverse Events, Pregnancy, and Events Associated with Special Situations

9.5.4.1 Reporting of Serious Adverse Events

All SAEs, regardless of their relationship to study treatment, must be reported on a completed SAE form by email or fax as soon as possible but no later than 24 hours from when the investigator becomes aware of the event.

SAEs, regardless of causality assessment, must be collected up to 12 weeks after the last dose of study drug. All SAEs must be followed to resolution or, if resolution is unlikely, to stabilization. Any SAE judged by the investigator to be related to the study treatment or any protocol-required procedure should be reported to the sponsor regardless of the length of time that has passed since study completion.

The detailed contact information for reporting of SAEs is provided in the Investigator Study File.

For urgent safety issues, please ensure all appropriate medical care is administered to the subject and contact the appropriate study team member listed in the Investigator Study File.

It is very important that the SAE report form be filled out as completely as possible at the time of the initial report. This includes the investigator's assessment of causality.

Any follow-up information received on SAEs should be forwarded within 1 business day of its receipt. If the follow-up information changes the investigator's assessment of causality, this should also be noted on the follow-up SAE form.

Preliminary SAE reports should be followed as soon as possible by detailed descriptions including copies of hospital case reports, autopsy reports, and other documents requested by the sponsor.

The investigator must notify his/her IRB/IEC of the occurrence of the SAE in writing, if required by their institution. A copy of this communication must be forwarded to the sponsor, or its designee, to be filed in the sponsor's Trial Master File.

9.5.4.2 Reporting of Pregnancy and Exposure to Study Drug Through Breastfeeding

Any pregnancy in which the estimated date of conception is either before the last visit or within 28 days of last study treatment, or any exposure to study drug through breastfeeding during study treatment or within 28 days of last study treatment, must be reported.

If an adverse outcome of a pregnancy is suspected to be related to study drug exposure, this should be reported regardless of the length of time that has passed since the exposure to study treatment.

A congenital anomaly, death during perinatal period, an induced abortion, or a spontaneous abortion are considered to be an SAE and should be reported in the same time frame and in the same format as all other SAEs (see Reporting of SAEs [Section 9.5.4.1]).

Pregnancies or exposure to study drug through breastfeeding must be reported by fax or email as soon as possible but no later than 1 business day from the date the investigator becomes aware of the pregnancy. The contact information for the reporting of pregnancies and exposure to study drug through breastfeeding is provided in the Investigator Study File. The Pregnancy Report Form must be used for reporting. All pregnancies must be followed to outcome. The outcome of the pregnancy must be reported as soon as possible but no later than 1 business day from the date the investigator becomes aware of the outcome.

A subject who becomes pregnant must be withdrawn from study treatment.

Pregnancies in partners of male study subjects do not need to be reported. (revised per Amendment 03)

9.5.4.3 Reporting of Events Associated with Special Situations

9.5.4.3.1 REPORTING OF ADVERSE EVENTS ASSOCIATED WITH STUDY DRUG OVERDOSE, MISUSE, ABUSE, OR MEDICATION ERROR

AEs associated with study drug overdose, misuse, abuse, and medication error refer to AEs associated with uses of the study drug outside of that specified by the protocol. Overdose, misuse, abuse, and medication error are defined as follows:

Overdose	Accidental or intentional use of the study drug in an amount higher than the protocol-defined dose
Misuse	Intentional and inappropriate use of study drug not in accordance with the protocol
Abuse	Sporadic or persistent intentional excessive use of study drug accompanied by harmful physical or psychological effects

Medication error Any unintentional event that causes or leads to inappropriate study drug use or subject harm while the study drug is in the control of site personnel or the subject.

All AEs associated with overdose, misuse, abuse, or medication error should be captured on the Adverse Event eCRF and also reported using the procedures detailed in Reporting of SAEs (Section 9.5.4.1) even if the AEs do not meet serious criteria. Abuse is always to be captured as an AE. If the AE associated with an overdose, misuse, abuse, or medication error does not meet serious criteria, it must still be reported using the SAE form and in an expedited manner but should be noted as nonserious on the SAE form and the Adverse Event eCRF.

Subjects will be monitored for AEs that may signal drug abuse potential during the Treatment Period and the first 4 weeks of the Follow-up Period. Examples of AEs that may signal drug abuse potential are provided in Appendix 3. A detailed listing of AEs that may signal drug abuse potential is provided in the E2909-G000-301 eCRF Completion Guidelines. (revised per Amendment 03)

9.5.4.3.2 REPORTING OF STUDY-SPECIFIC EVENTS

Study-specific events (as detailed in Section 9.5.1.5.2) should always be considered as serious important medical events and be entered on the Adverse Event eCRF and reported using the procedures detailed in Reporting of SAEs (Section 9.5.4.1), even if the study-specific event does not meet other serious criteria.

9.5.4.4 Expedited Reporting

The sponsor must inform investigators (or as regionally required, the head of the medical institution) and regulatory authorities of reportable events, in compliance with applicable regulatory requirements, on an expedited basis (ie, within specific time frames). For this reason, it is imperative that sites provide complete SAE information in the manner described above.

9.5.4.5 Breaking the Blind

In the case of a medical emergency where the appropriate treatment of the subject requires knowledge of the study treatment given, the investigator may break the randomization code for an individual subject. In all such cases, the AE necessitating the emergency blind break will be handled as an SAE in accordance with the procedures indicated above. Any broken code will be clearly justified and documented. The medical monitor must be notified immediately of the blind break.

9.5.4.6 Regulatory Reporting of AEs

AEs will be reported by the sponsor or a third party acting on behalf of the sponsor to regulatory authorities in compliance with local and regional law and established guidance. The format of these reports will be dictated by the local and regional requirements.

All studies that are conducted within any European country will comply with European Good Clinical Practice Directive 2005/28/EC and Clinical Trial Directive 2001/20/EC. All SUSARs will be reported, as required, to the competent authorities of all involved European member states.

9.5.5 Completion/Discontinuation of Subjects

A subject may elect to withdraw from the study at any time for any reason. All subjects who discontinue study drug early for any reason will undergo an ED Visit within 7 days of their last dose of study drug (see [Section 9.1.2.2](#)). In addition, Follow-Up Visits will be scheduled 4 and 12 weeks after the last dose of study drug (Visit 14 and Visit 15, respectively) (see [Section 9.1.2.2](#)). These Follow-Up Visits will be conducted to monitor efficacy and safety parameters after early withdrawal from the study or discontinuation of study drug. See [Table 4](#) for full details of the assessments to be performed at these visits.

All subjects who discontinue study drug before reaching 12 months of treatment will also be asked to return to the clinic for a 12 month clinical assessment and then again at 24 months. Subjects who discontinued treatment between 12 and 24 months of treatment will be asked to return to the clinic for a 24 month clinical assessment. Subjects who discontinue early from study drug are considered “on study” as long as they continue to return for their clinical assessments at 12 and 24 months as outlined above, at which efficacy and quality of life will be assessed along with concomitant medications and AEs. However, subjects who discontinue study drug early are not considered to have ‘completed’ the study as a final Subject Disposition. A subject removed from the study for any reason may not be replaced.

The investigator will promptly explain to the subject involved that the study will be discontinued for that subject and provide appropriate medical treatment and other necessary measures for the subject. A subject who has ceased to return for visits will be followed up by mail, phone, or other means to gather information such as the reason for failure to return, the status of treatment compliance, the presence or absence of AEs, and clinical courses of signs and symptoms.

The primary reasons for early withdrawal from the study are: AE, lost to follow-up, subject choice, withdrawal of consent, pregnancy, study terminated by sponsor, and other. The secondary reasons for early withdrawal from the study are: AE, subject choice, and other.

The primary reasons for early discontinuation from the study drug are: AE, subject choice, pregnancy, inadequate therapeutic effect, and other. The secondary reasons for early discontinuation from the study drug are: AE, subject choice, inadequate therapeutic effect, and other.

9.5.6 Abuse or Diversion of Study Drug

AEs associated with abuse or diversion will be appropriately reported as AEs and monitored per [Section 9.5.1.5.1](#). Abuse is always to be captured as an AE.

During the study, the investigator should be aware of the possibility of abuse or diversion of study drugs and should report any concern about mishandling, abuse, loss, theft, or diversion of study drugs by completing the Abuse or Diversion of Study Drug eCRF.

9.5.7 Confirmation of Medical Care by Another Physician

The investigator will instruct subjects to inform site personnel when they are planning to receive medical care by another physician. At each visit, the investigator will ask the subject whether he or she has received medical care by another physician since the last visit or is planning to do so in the future. When the subject is going to receive medical care by another physician, the investigator, with the consent of the subject, will inform the other physician that the subject is participating in the clinical study.

9.6 Data Quality Assurance

This study will be organized, performed, and reported in compliance with the protocol, standard operating procedures, working practice documents, and applicable regulations and guidelines. Site audits will be made periodically by the sponsor's or the CRO's qualified compliance auditing team, which is an independent function from the study team responsible for conduct of the study.

9.6.1 Data Collection

Data required by the protocol will be collected on the eCRFs and entered into a validated data management system that is compliant with all regulatory requirements. As defined by ICH guidelines, the CRF is a printed, optical, or electronic document designed to record all of the protocol-required information to be reported to the sponsor on each study subject.

Data collection on the eCRF must follow the instructions described in the CRF Completion Guidelines. The investigator has ultimate responsibility for the collection and reporting of all clinical data entered on the eCRF. The investigator or designee as identified on Form FDA 1572 (where applicable) must sign the completed eCRF to attest to its accuracy, authenticity, and completeness.

Completed, original eCRFs are the sole property of Eisai and should not be made available in any form to third parties without written permission from Eisai, except for authorized representatives of Eisai or appropriate regulatory authorities.

9.6.2 Clinical Data Management

All software applications used in the collection of data will be properly validated following standard computer system validation that is compliant with all regulatory requirements. All data, both eCRF and external data (eg, laboratory data), will be entered into a clinical system.

Electronic source (eSource) methodology may be used for some of the clinical efficacy and HRQoL assessments performed in this study.

9.7 Statistical Methods

All statistical analyses will be performed by the sponsor or designee. Statistical analyses will be performed using SAS software or other validated statistical software as required.

All statistical tests will be based on the 5% (2-sided) level of significance, unless specified.

9.7.1 Statistical and Analytical Plans

All statistical analyses will be performed by the Sponsor or designee after the study is completed and the database is locked and released for unblinding.

9.7.1.1 Study Endpoints

9.7.1.1.1 PRIMARY ENDPOINT

The primary endpoint of the study is:

- Change from baseline in the CDR-SB at 24 months.

9.7.1.1.2 SECONDARY ENDPOINTS

The secondary endpoints of the study are:

- Time to worsening of CDR scores by 24 months (eg, the worsening of global CDR score is defined as an increase from baseline by at least 0.5 points on the global CDR scale on 2 consecutive scheduled visits at which global CDR is undertaken)
- Time to conversion to dementia for subjects who were not clinically staged as dementia at Baseline based on clinical diagnosis
- The rate of change over time (mean slope) based on CDR-SB score over 24 months
- Change from baseline in CDR-SB at 27 months (ie, 24 months of treatment plus 3 months posttreatment follow-up)
- Change from baseline in ADAS-cog₁₄, MMSE, and FAQ at 24 months
- Change from baseline in ADAS-cog₁₄ Word List (immediate recall and delayed recall) at 24 months

9.7.1.1.3 EXPLORATORY ENDPOINTS

The exploratory endpoints of the study are:

- Time to change of concomitant AD treatment (ie, dose increase and/or initiation of treatment with AChEI or memantine after randomization) by 24 months
- The proportion of subjects at 24 months who received dose increases and/or initiation of treatment with AChEI or memantine after randomization
- The rate of change over time (mean slope) based on NPI-10 item score over 24 months
- Change from baseline in NPI-10 item at 24 months
- Change from baseline in EQ-5D (subject self-reported, study partner self-reported, and subject measured by proxy) and QOL-AD (subject and study partner) at 24 months
- Change from baseline in Zarit's Burden Interview at 24 months

9.7.1.1.4 BIOMARKERS ENDPOINTS

The biomarker endpoints for this study are:

- Change from baseline in amyloid PET SUVR composite at 24 months for brain amyloid levels
- Change from baseline in CSF biomarkers t-tau and p-tau at 24 months
- Change from baseline in CSF amyloid biomarkers A β (1-42), and A β (1-x) at 24 months (revised per Amendment 03)
- Change from baseline in total hippocampal volume at 24 months using vMRI
- Change from baseline in the preservation of connectivity on fMRI at 24 months

9.7.1.2 Definitions of Analysis Sets

- The Randomized Set is the group of subjects who are randomized to study drug.
- The Safety Analysis Set is the group of subjects who receive at least 1 dose of study drug and have at least 1 postdose safety assessment.
- The Full Analysis Set (FAS) is the group of randomized subjects who receive at least 1 dose of study drug and have baseline and at least 1 postdose primary efficacy measurement.
- The Per Protocol Analysis Set (PPS) is the subset of subjects in the FAS who sufficiently comply with the protocol. The PP Analysis Set will be used to conduct a sensitivity analysis of the primary efficacy endpoint. Details of the evaluability criteria will be determined before database lock and treatment unblinding, and will be specified in the statistical analysis plan.

- The PK Analysis Set is the group of subjects with at least 1 quantifiable elenbecestat (E2609) plasma concentration with a documented dosing history.
- The PD Analysis Set is the group of subjects who have sufficient PD data to derive at least 1 PD parameter.

9.7.1.3 Subject Disposition

The number of subjects screened, the number (percent) of subjects who failed screening, and the reasons for screen failure will be summarized, based on data reported on the Screening Disposition eCRF. The distribution of the number of randomized subjects enrolled by each site will be summarized for each randomized treatment group. The primary reasons for screen failures (did not meet inclusion or met exclusion criteria, AE, lost to follow-up, withdrawal of consent, and other) will be presented.

Study Completion: the number (percent) of randomized and treated subjects who completed the study and who discontinued from the study will be summarized according to the primary reason for discontinuation and secondary reason(s) for discontinuation, based on data reported on the Subject Disposition (Study Phase) CRF. The number (percent) will be presented by treatment group and total for subjects; randomized, not treated, treated, who completed the study, and discontinued from the study. The primary reasons for early withdrawal from the study are: AE, lost to follow-up, subject choice, withdrawal of consent, pregnancy, study terminated by sponsor, and other. The secondary reasons for early withdrawal from the study are: AE, subject choice, and other.

Completion of Study Treatment: the number (percent) of randomized and treated subjects who completed study drug and who discontinued from study drug will be summarized according to the primary reason for discontinuation and also according to secondary reason(s) for discontinuation, based on data reported on both the Subject Disposition (Study Phase) eCRF and ED from Study Drug eCRF. The number (percent) will be presented by treatment group and total for subjects; randomized, not treated, treated, who completed study drug, and discontinued from study drug. The primary reasons for early discontinuation from the study drug are: AE, subject choice, pregnancy, inadequate therapeutic effect, and other. The secondary reasons for early discontinuation from the study drug are: AE, subject choice, inadequate therapeutic effect, and other.

9.7.1.4 Demographic and Other Baseline Characteristics

Demographic and other baseline characteristics for the Safety Analysis Set and FAS will be summarized for each treatment group using descriptive statistics. Continuous demographic and baseline variables include age, CDR scores, ADAS-cog₁₄, MMSE and FAQ; categorical variables include sex, age group (equal or less than 65 years, age greater than 65 years), race, ethnicity, region, *ApoE4* genotype, prior treatment with AChEIs or memantine (no or yes), and clinical subpopulation (MCI due to AD or the early stages of mild AD).

9.7.1.5 Prior and Concomitant Therapy

All investigator terms for medications recorded in the eCRF will be coded to an 11-digit code using the World Health Organization Drug Dictionary (WHO DD) (Mar 2014). The number (percentage) of subjects who took prior and concomitant medications will be summarized on the Safety Analysis Set by treatment group, Anatomical Therapeutic Chemical class, and WHO DD preferred term (PT). Prior medications will be defined as medications that stopped before the first dose of study drug. Concomitant medications will be defined as medications that (1) started before the first dose of study drug and were continuing at the time of the first dose of study drug, or (2) started on or after the date of the first dose of study drug up to the date of the last dose. All medications will be presented in subject data listings.

Medications taken within the 12-week Follow-Up Period will also be recorded.

9.7.1.6 Efficacy Analyses

The FAS will be used as the primary population for all efficacy analyses, while the PPS will be used as the supportive population.

9.7.1.6.1 PRIMARY EFFICACY ANALYSIS

The primary analysis will be based on an intent to treat philosophy without regard to adherence to treatment. The primary analysis of the change from baseline in CDR-SB at 24 months will be performed to compare elenbecestat (E2609) 50 mg per day versus placebo using a linear mixed effects model for repeated measures (MMRM) on the FAS. The MMRM model will include baseline CDR-SB as a covariate, with treatment group, visit, randomization stratification variables (ie, region [7 levels], clinical dementia [yes, no], and concurrent AD medication use at randomization (Visit 2) [yes, no]), and treatment group-by-visit interaction as fixed effects. An unstructured covariance matrix will be employed to model the covariance of within subject effect; if MMRM fails to converge then a covariance structure with fewer parameters from the following list will be employed according to the prespecified order in the list until the MMRM converges. The list of covariance structure will include Heterogeneous Toeplitz, Toeplitz, Heterogeneous Compound Symmetry, and Compound Symmetry. This primary analysis will include all observed post baseline data of the change from baseline in CDR-SB without imputation of missing values. The treatment effect for elenbecestat (E2609) versus placebo will be compared at 24 months based on MMRM model. The LS means and difference in LS means between elenbecestat (E2609) treatment group and placebo, and corresponding 95% CI will be presented.

The null hypothesis is that there is no difference in the mean change from baseline in CDR-SB at 24 months between elenbecestat (E2609) 50 mg per day and placebo. The corresponding alternative hypothesis is that there is a difference in the mean change from baseline in CDR-SB at 24 months between elenbecestat (E2609) 50 mg per day and placebo.

The primary analysis will be repeated to minimize the impact of change in concomitant AD medications where efficacy data after initiation of new AD medications and increase of current AD medications will be censored.

The following sensitivity analysis will be conducted to evaluate the impact of missing data: the primary endpoint will be analyzed using ANCOVA after multiple imputation. The ANCOVA model will include baseline CDR-SB as a covariate, with treatment group and randomization stratification variables as factors.

Subgroup analysis (eg, *ApoE4* genotype) and additional sensitivity analysis for the primary endpoint will be performed as appropriate.

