9.1.2.1 Treatment Period

During Visit 2, the following assessments will be completed before the subject receives their first dose of study drug: MMSE, CDR, ADAS-cog₁₄, FAQ, and NPI-10. These assessments will provide baseline measurements for the study. For any given subject, every effort should be made to ensure that the CDR rater remains unchanged throughout the study. (revised per Amendment 03) Inclusion and exclusion criteria will again be reviewed together with

concomitant medications and assessment of AEs. A single 12-lead ECG will be conducted. All ECG recordings will be evaluated by a central reader. The Columbia-Suicide Severity Rating Scale (C-SSRS) will also be administered. A baseline routine physical examination with dermatologic review, vital signs measurements, clinical laboratory testing (including viral characterization), urinalysis using urine dipstick, and a urine pregnancy test (females of child-bearing potential only), will be performed. Additional blood samples will be taken for PD/exploratory biomarkers and immunologic assessments. (revised per Amendment 03) Some of the immunologic assessment blood sample will be used to prepare isolated peripheral blood mononuclear cells (PBMCs) which will be stored for testing as needed. (revised per Amendment 02) The results of some of the immunologic assessments will be provided to the DSMB for periodic review during the study. Whilst there is no prescribed order in which the assessments at each visit are to be performed, the subject component of the cognitive, functional and quality of life assessments are to be performed in the morning whenever possible, or consistently at the same time of the day and ideally should be completed before the more invasive procedures (eg, physical examination, ECG, blood draw).

Subjects will be randomized at Visit 2 (Day 1) to receive elenbecestat (E2609) 50 mg per day or placebo administered orally QD in the morning with or without food. Subjects will be encouraged to stay at the site for observation for at least 30 minutes following their first dose of study drug. The duration of this observation period can be extended at the Investigator's discretion, eg, if warranted by medical history or concomitant medication. (revised per Amendment 03) Double-blinding to study drug will be in effect throughout the Treatment Period.

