9.3.1 Inclusion Criteria

Subjects must meet all of the following criteria to be included in this study:

1. MCI due to AD or Mild AD according to the National Institute of Aging – Alzheimer’s Association (NIA-AA) core clinical criteria and must have all of the following at Screening: (revised per Amendment 03)
 - a. MMSE score equal to or greater than 24
 - b. CDR global score of 0.5
 - c. CDR Memory Box score of 0.5 or greater
2. A history of subjective memory decline with gradual onset and slow progression over the last 1 year before Screening; this MUST be corroborated by a study partner
3. Cognitive impairment of at least 1 SD from age-adjusted norms in total recall or delayed recall on the ISLT.

4. Positive biomarker for brain amyloid pathology as indicated by at least 1 of the following:
 - a. PET assessment of amyloid imaging agent uptake into brain. Note: amyloid PET screens will be performed according to local regulatory guidelines and thus may be restricted for those subjects who are not suitable for LP to obtain CSF for testing of eligibility.
 - b. CSF AD assessment (eg, A β (1-42), tau: A β (1-42) ratio) (revised per Amendment 03)
NOTE: Subjects may undergo both the amyloid PET and CSF assessments, but need a positive amyloid result in only 1 of the 2 procedures to confirm eligibility. Subjects who consent to amyloid PET or CSF for eligibility purposes are not required to participate in the amyloid PET or CSF longitudinal substudies. Use of a historical amyloid positive PET (conducted within 12 months before the planned date of randomization) is acceptable for determination of eligibility but will not suffice for the baseline assessment if the subject wishes to consent to the amyloid PET longitudinal substudy. (revised per Amendment 03) The historical imaging data must be made available to the sponsor.
5. Male or female subjects between 50 and 85 years of age, inclusive at the time of consent
6. If receiving an AChEI or memantine or both for AD, must be on a stable dose for at least 12 weeks prior to Randomization. Treatment-naïve subjects with AD can be entered into the study.

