9.7.2 Determination of Sample Size

The sample size for this study is estimated based on comparison of elenbecestat (E2609) versus placebo with respect to the primary efficacy endpoint, the change from baseline CDR-SB at 24 months. Based on available ADNI data [amyloid positive, MMSE equal or greater than 24, late MCI (global CDR=0.5) populations from ADNI, ADNI 2 and ADNI GO] the mean and the standard deviation of the change from baseline in the CDR-SB at 24 months in the placebo group are assumed to be 1.75 and 2.05, respectively. Therefore, assuming a 25% reduction in the mean change from baseline CDR-SB at 24 months for the elenbecestat (E2609) 50 mg per day dose group compared to placebo with a common standard deviation of 2.05 and an estimated 30% dropout rate in this study, a total sample size of 1330 subjects, 665 subjects in each treatment group, will be required to detect the treatment difference between elenbecestat (E2609) 50 mg per day and placebo using a 2-sample t-test with 90% power at a significance level of 2-sided $\alpha=0.05$.

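### The primary MMRM is valid and keeps its 90% power, but it adjusts only for baseline CDR-SB and the strata; adding baseline covariates already collected, each with a visit interaction, would be a free gain in precision

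*Protocol*

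**What the plan says.** The Protocol, section 9.7.1.6.1, sets out the primary MMRM for change in CDR-SB at 24 months: "The MMRM model will include baseline CDR-SB as a covariate, with treatment group, visit, randomization stratification variables", with the treatment-by-visit interaction. The strata are region (7 levels), clinical dementia (yes/no) and concurrent AD medication (yes/no). No other baseline variable is named, and no covariate-by-visit term is listed. All observed post-baseline values enter without imputation.

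The same protocol collects more than this before treatment starts:

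- Section 9.1.2.1 has MMSE, CDR, ADAS-cog14, FAQ and NPI-10 done at Visit 2 before the first dose and says of them: "These assessments will provide baseline measurements for the study".
- Section 9.7.1.4 already tabulates such variables: "Continuous demographic and baseline variables include age, CDR scores", followed by ADAS-cog14, MMSE and FAQ, with ApoE4 genotype among the categorical ones.
- Table 1 in section 9.5.1.4.2 marks ApoE as mandatory for all subjects. Appendix 4 makes an exception where country law forbids collecting or using the sample.

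Entry is restricted on severity. Section 9.3.1 requires at Screening a "CDR global score of 0.5", a memory box of at least 0.5 and an MMSE of at least 24.

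**The concern.** A baseline variable that predicts 24-month decline reduces the residual variance of the treatment contrast at no cost in subjects. Here the only continuous covariate is baseline CDR-SB, whose range is cut by the entry rule on global CDR. As the model terms are listed, it also has a single coefficient for every visit from month 3 to month 24. Cognitive and functional scales measured at the same visit, and age, are left unused.

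Two things are at stake. One is precision, which matters more if the SD proves larger than assumed; section 9.7.3 itself says that this is possible. The other is robustness to missing data. With 30% dropout planned, the MMRM relies on data being missing at random given what is in the model, and a richer baseline set widens what is conditioned on.

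**Working it through.** **Reproducing the planned size.** Inputs from sections 9.7 and 9.7.2:

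- Level: "All statistical tests will be based on the 5% (2-sided) level of significance, unless specified".
- Test and power: "using a 2-sample t-test with 90% power at a significance level of 2-sided" alpha of 0.05.
- Placebo mean and SD of change: "in the placebo group are assumed to be 1.75 and 2.05, respectively".
- Effect: "assuming a 25% reduction in the mean change from baseline CDR-SB at 24 months", so 0.25 × 1.75 = 0.4375 points.
- Dropout 30%; 1330 randomized, 665 per arm.

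n per arm = 2(1.960 + 1.282)² × 2.05² / 0.4375² = 462. Dividing by 0.70 gives 660 per arm, 1320 in total. The exact t calculation gives 463, then 662 per arm, 1324 in total. The stated 1330 is reproduced to within rounding.

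Evaluable per arm: 665 × 0.70 = 465. SE = 2.05 × √(2/465) = 0.1344, and exact t power is 90.2%. This uses the raw SD and borrows nothing from covariates.

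**Gain from added covariates.** Let R² be the extra share of month-24 residual variance explained. The documents give no value, so a range is assumed. Residual SD = 2.05 × √(1 − R²); SE = residual SD × √(2/465); the equivalent number randomized is 1330/(1 − R²).

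| Assumed R² | Residual SD | SE | Power | Equivalent N |
|---|---|---|---|---|
| 0 | 2.050 | 0.1344 | 90.2% | 1330 |
| 0.02 | 2.029 | 0.1331 | 90.7% | 1357 |
| 0.05 | 1.998 | 0.1310 | 91.5% | 1400 |
| 0.10 | 1.945 | 0.1275 | 92.9% | 1478 |
| 0.15 | 1.890 | 0.1240 | 94.1% | 1565 |

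If the SD were 2.3 (assumed), power would be 82.7% without the covariates and 86.4% with R² = 0.10.

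**Why the visit interaction matters.** The table assumes the covariate effect is fitted freely at month 24. Suppose instead that the true effect grows linearly with time, reaching b at month 24 with b² = R² × 2.05², while the model allows one constant coefficient equal to λb. The residual variance at month 24 is then 2.05²(1 − R²) + b²(1 − λ)². The value of λ depends on the within-subject covariance, which must also be assumed (eight visits, complete data). At R² = 0.10:

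- Random slope plus noise, with 80% of month-24 variance from the slope: λ = 0.171. Variance = 3.782 + 0.420 × 0.829² = 4.071, SD 2.018, power 91.0%.
- First-order autoregressive (0.8), SD rising linearly with time from 0.56 of its month-24 value at month 3: λ = 0.337. Variance = 3.782 + 0.420 × 0.663² = 3.967, SD 1.992, power 91.7%.
- First-order autoregressive (0.9), constant SD: λ = 0.607. Variance = 3.782 + 0.420 × 0.393² = 3.847, SD 1.961, power 92.5%.

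So main effects alone can lose more than half of the gain from 90.2% to 92.9% when spread grows over time, and little when it does not.

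**Missing data.** A simulation used 665 per arm, eight visits, monotone dropout of about 25% to 28%, a true difference of −0.4375, an omitted covariate explaining 5% to 20% of month-24 variance, and 400 runs per setting (Monte Carlo error about 0.006).

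- Covariate drives dropout equally in both arms: the planned model gives −0.440 to −0.442, so no detectable bias.
- Covariate drives dropout in the active arm only (log-odds 0.5 to 1.0 per SD): the planned model gives −0.459 to −0.560. With the covariate added, the estimate is −0.430 to −0.456.

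**The case against.** The strongest case against raising this is that nothing is wrong. The model is prespecified and adjusts for the baseline outcome and every stratification factor, and the trial was sized on an unadjusted t-test. A longer covariate list is a preference, and its benefit rests on an R² that the documents do not supply. All of that stands, and it is why the point is optional.

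A reader might also infer several stronger things that the documents do not support:

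- *That baseline CDR-SB is nearly constant and can explain little.* The entry rule fixes the global CDR at Screening. The covariate is the six-box sum, on a 0 to 18 scale, measured again at Visit 2, and the memory box has no stated upper limit. It is range-restricted only. MMSE is restricted at entry too.
- *That the protocol itself calls ApoE4 and ADAS-cog14 prognostic for CDR-SB.* Section 9.2.4 speaks of explaining differences in treatment response, which is effect modification. Section 9.2.3 defends ADAS-cog14 and FAQ as outcome measures.
- *That the omission biases the primary estimate.* The MMRM already conditions on each subject's observed CDR-SB, and subjects who stop drug are asked back at 12 and/or 24 months (section 9.3.3). Bias appeared only under assumed arm-specific dropout. Such dropout is conceivable, since section 9.3.3 stops drug for repeated confirmed lymphocytopenia or suspected drug rash, but nothing shows that these covariates drive it.
- *That every subject will have ApoE.* Appendix 4 allows exceptions by country law, so missing values may cluster by country.

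**Conclusion.** The point holds as an efficiency and robustness suggestion. The primary MMRM is valid and delivers its stated 90% power (90.2% recomputed), so a reader should not conclude that the trial is underpowered or the analysis flawed. Prognostic information already in hand is left out. Depending on an assumed extra R² of 2% to 15%, using it would lift power to somewhere between about 90.7% and 94.1%, and by less without covariate-by-visit terms. The missing-data benefit is confined to dropout that depends on these covariates differently by arm; with equal dependence none was detectable. The sizes rest on the protocol's SD of 2.05 and 465 evaluable per arm, and on R² and covariance values that the documents do not give.

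**What to change.** Before any unblinded look, including the futility analysis planned when 30% of subjects have completed 24 months, prespecify these in the primary MMRM:

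- baseline ADAS-cog14, baseline FAQ and age;
- ApoE4 carrier status, with a missing category where genotyping is barred by country law;
- a covariate-by-visit interaction for each of these and for baseline CDR-SB.

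Use the same list in the MMRMs for the continuous secondary endpoints and in the multiple-imputation model of the sensitivity analysis. MMSE can be left off to keep the list short.

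The cost is wording in the protocol or SAP and a somewhat larger model. No new data, visits or subjects are needed.
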